2. To determine the duration of analgesia produced by N2O in the aforementioned population.

Study Design:

We will conduct a single center pilot study in the pediatric emergency department (PED) of an urban, tertiary care children's hospital. The study is an interdivisional study between pediatric emergency medicine ([name]) and pediatric hematology ([name]).

Patient demographics for each patient will be documented, and a baseline neurological exam performed by the attending pediatric emergency medicine physician responsible for their care during that PED visit. An 8-week follow up physical examination will be performed if vitamin B12 levels obtained during the PED visit are low (see STUDY PROCEDURES: Follow-up Procedures). Vitamin B12 levels are being done solely for the conduct of this research. Our primary outcome will be the change in pain score from just prior administration to immediately following the discontinuation of N2O. The pain score will be measured using a numeric rating scale (NRS) of 0 (no pain) to 10 (worst pain), which is a valid and responsive scale for measuring pain in children older than 8 years of age. Our secondary outcomes will include:

- 1) the duration of analgesia resulting from N2O, which will be defined as the time elapsed from the discontinuation of N2O to the time at which the pain score becomes $>$ or $= 7/10$ (for those whose score decreased below 7), the patient receives additional analgesia, is discharged home, or is admitted to hospital. This time will be measured in minutes. Additional secondary outcomes will include,

2) complaints or physical findings suggestive of peripheral neuropathies (which may present as numbness, tingling, pain, or loss of feeling in fingers or toes; or weakness or difficulty moving the arms or legs) at the 8 week follow-up, as well as,

3) the presence of macrocytic anemia at 8 weeks time in patients who had low vitamin B12 levels at the time of enrolment.

STUDY PROCEDURES

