- A) The following procedure is STANDARD care: Patients with SCD who present to the ED with VOC and a pain score of $\geq 7/10$ (i.e. severe pain) will receive IV fluids, NSAIDs, and IV morphine or hydromorphone. Blood work will be drawn and includes CBC, reticulocytes, and type and screen. After administration of the analgesics, the patient's pain will be reassessed after 15 minutes. If pain is still $\geq 7/10$, the patient will receive a "rescue" dose of IV morphine or hydromorphone. The patient's pain will be reassessed every 15 minutes and IV morphine or hydromorphone will be repeated until the pain score is $< 7/10$, at which point the patient's pain is reassessed (usually at least once every hour – there is no standardized interval) and the patient is transitioned to an oral analgesic at the attending physician's discretion, in conjunction with the hematology service.
- B) The following procedure is for RESEARCH purposes: Patients with SCD will be identified by a research assistant or study investigator if they have VOC and a pain score of $\geq 7/10$. If the patient has not already been consented (see informed consent), the primary physician providing care for the patient in the ED will be approached and asked to approach the patient and family to see if they would be interested in participating in the study. If they say yes, then a study investigator will approach the family to obtain informed consent. The reason why the family is approached at this point in time is so that the N2O treatment can be immediately initiated if the initial standard treatment is not effective, and so that there is no delay in care in providing analgesia when they have severe pain.

The patient will still receive the standard care of IV fluids, NSAIDs, and IV morphine or hydromorphone. In addition to the standard blood work, a vitamin B12 level will be drawn for study purposes. An additional 1 mL of blood (less than a quarter of a teaspoon) will be required. The pain score will be reassessed 15 minutes after the initial is still $\geq 7/10$, we will administer N2O at a concentration of 50% for 20 minutes. N2O is approved for use in the pediatric emergency department as per NYP Policy S100, and all standard procedures for administration and monitoring as per this policy will be followed.

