Five minutes after discontinuation of the N2O, the patient's pain score will be assessed. If the pain score is still $\geq 7/10$, the patient will receive a "rescue" dose of IV morphine or hydromorphone, similar to the procedure in standard care, and will continue to be treated as per standard care.

If the patient's pain is $< 7/10$, the patient will have their pain reassessed by a study investigator every 15 minutes for the first hour, and then every 30 minutes after the first hour is completed OR whenever the patient volunteers or requests a pain assessment. Pain assessments will continue until the patient is discharged home. This frequency of pain assessment is the same, if not more frequent, than what occurs in standard care. The primary attending, in conjunction with the hematology service, will determine the transition to an oral analgesic and when to discharge the patient home.

- C) The following follow-up procedure is for RESEARCH purposes: Within 48 hours of the ED visit, a study investigator will review the laboratory results drawn at the time of enrollment. If the vitamin B12 level is

normal, then a study investigator or research coordinator will conduct a follow-up telephone call at week 8 to assess for any neurological symptoms. If the vitamin B12 level is low, the study investigators will notify the patient's attending hematologist within 24 hours and a follow up appointment will be scheduled at 8 weeks post enrollment at an outpatient clinic (hematology clinic or CTSA outpatient resource [if approved]). During this visit, one of the study investigators will conduct a physical examination and obtain laboratory tests (CBC and differential, vitamin B12) to evaluate for any potential long term side effects of receiving N2O (e.g. peripheral neuropathies, megaloblastic anemia).(7,17) Of note, the chances of these adverse events are low; they do not present acutely (onset is typically between 1 to 8 weeks); they are completely reversible with vitamin B12 supplementation; and have only been reported in the context of severe vitamin B12 deficiency and prolonged and repeated N2O administration.(7,17,18) Sickle cell patients are not expected to have vitamin B12 deficiency that would predispose them to these adverse events.(19) In discussion with our hematologists at NYP, it is their experience that our population of patients with SCD are at low risk of being deficient in vitamin B12.

Statistical Procedures:

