Sample size: Twelve patients will be analyzed for this pilot study. This sample size was selected as there is minimal increase in precision expected around the mean and variance in the pain score change with additional patients enrolled. (16) To meet this analysis sample size, we anticipate that we may enroll up to 24 patients with severe VOC. This is because we expect that 50% of patients who are consented will ultimately not fulfill all inclusion criteria (i.e. their pain may be adequately managed with initial standard treatment, and may not require additional parenteral analgesia). The experience at our institution is that approximately 53% of patients with SCD who present to the PED with a VOC requiring parenteral analgesia as initial standard treatment require additional parenteral analgesics. We will not wait until patients have demonstrated a need for additional analgesia to begin the consent process, as this would delay the administration of analgesia in a patient with severe pain.

Statistical Plan: To assess the primary outcome, the mean difference and standard deviation in pain score before and immediately after N2O administration will be calculated for the NRS. Assessment of the secondary outcomes will be performed as follows:

- 1) the duration of analgesia will be determined by calculating the mean time and standard deviation (minutes) after discontinuation of N2O administration until the time at which the pain score becomes $>$ or $= 7/10$, the patient receives additional parenteral analgesia, is discharged home, or is admitted to hospital. The pain scores for each patient will also be plotted on a chart to illustrate the change in pain over time (y-axis = pain score, x-axis = time).
- 2) The presence of signs or symptoms suggestive of peripheral neuropathies will be documented, and the proportion calculated.
- 3) The presence of macrocytic anemia, if patients who have a low initial vitamin B12 level (see STUDY PROCEDURES: Follow-up Procedures) will also be documented and the proportion calculated.

Potential Risks:

There is limited data on the risks associated with N2O in patients with SCD. There are reports of long term side effects such as peripheral neuropathies and megaloblastic anemia).(7,17) The chances of these adverse events are low and have only been reported in case reports. They do not present acutely (onset is typically between 1 to 8 weeks), are completely reversible with vitamin B12 supplementation, and have only been

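### The planned mean duration of analgesia counts leaving the ED with pain below 7 as the end of relief, and its analgesia end point and its population are not settled

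*Combined protocol and SAP*

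**What the plan says.** Study Design, secondary outcome 1, starts the clock when N2O is stopped. It ends it when the score reaches 7 or more (with the parenthesis "for those whose score decreased below 7") or when "the patient receives additional analgesia, is discharged home, or is admitted to hospital".

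Statistical Procedures, Statistical Plan, item 1, gives the analysis: "the duration of analgesia will be determined by calculating the mean time and standard deviation (minutes) after discontinuation of N2O administration", ending at a score of 7 or more or when "the patient receives additional parenteral analgesia, is discharged home, or is admitted to hospital". The parenthesis is not repeated. The only other analysis is a plot: "The pain scores for each patient will also be plotted on a chart to illustrate the change in pain over time". No censoring rule or time-to-event method is named.

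Three points in Study Procedures bear on this:

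- Part A foresees, in standard care, that "the patient is transitioned to an oral analgesic at the attending" physician's discretion. Part B leaves both the oral transition and the timing of discharge to the attending with hematology.
- The first score comes "Five minutes after discontinuation of the N2O". A patient still at 7 or more then receives a rescue "dose of IV morphine or hydromorphone, similar to the procedure in standard care".
- Patients below 7 are scored every 15 minutes for an hour and every 30 minutes after that, or on request, until discharge home. Part B does not say whether scoring continues after admission.

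**The concern.** Aim 2 asks how long the analgesia from N2O lasts. Three features of the plan stop the reported mean from answering that.

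1. **Departure is treated as loss of relief.** Discharge or admission with pain below 7 gives a lower bound on duration, yet it enters the mean as a completed value. It falls mainly on patients whose relief lasts longest, and the time of discharge is a care decision.
2. **There are two analgesia end points.** An oral dose given with pain below 7 ends the duration under Study Design and does not end it under the Statistical Plan.
3. **The population is not stated.** If the parenthesis in Study Design restricts the whole outcome, non-responders drop out. If it qualifies only the return to 7, which is the more natural reading, non-responders stay in, because their rescue dose is itself an end point, at about 5 minutes.

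Two analysts could each follow the document and report different answers to Aim 2 from the same 12 patients.

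**Working it through.** **Inputs.** From the documents: 12 analysed patients, first score at 5 minutes, then the 15- and 30-minute schedule. They state no expected duration, departure time, oral-dose time or non-response rate, so there is no figure for this outcome to reproduce. (The one derived figure in the sample-size paragraph, enrolment of 12/(1 − 0.50) = 24, reproduces and is not affected.) Everything else below is an assumption.

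**Step 1: truncation by departure.** Let T be the true duration of relief, with mean m, and C the time of leaving. The plan averages min(T, C). Take C uniform from a to b minutes after N2O, independent of T.

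- T uniform on 0–180 (m = 90): for C up to 180, E[min(T, C)] = E[C] − E[C²]/360; for C above 180 it is 90. With C on 60–180, E[C] = 120 and E[C²] = 14,400 + 1,200 = 15,600, so the mean is 120 − 43.3 = 76.7, and 76.7/90 = 0.85.
- T exponential: E[min(T, C)]/m = 1 − m(e^(−a/m) − e^(−b/m))/(b − a). With median 120, m = 173.1. For C on 60–240 this is 1 − 173.1 × (0.707 − 0.250)/180 = 0.56.

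**Step 2: late detection.** Suppose pain return is seen only at scheduled scores (5, 20, 35, 50, 65 min, then every 30 min). Without requested scores this is an upper limit on lateness. It adds to each recorded duration, so it works against step 1. These ratios were simulated, with 1,000,000 draws per cell.

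Planned mean as a ratio to the true mean, for departure windows 60–180 / 60–240 / 120–360 min:

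| Assumed relief | Truncation only | With scheduled scoring |
|---|---|---|
| Uniform 0–180 | 0.85 / 0.90 / 0.99 | 0.93 / 1.00 / 1.12 |
| Triangular 0–90–180 | 0.90 / 0.94 / 0.997 | 0.99 / 1.04 / 1.14 |
| Exponential, median 60 | 0.73 / 0.79 / 0.92 | 0.81 / 0.88 / 1.03 |
| Exponential, median 120 | 0.49 / 0.56 / 0.73 | 0.52 / 0.59 / 0.78 |
| Exponential, median 180 | 0.36 / 0.43 / 0.59 | 0.38 / 0.45 / 0.62 |

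The net error runs from −7% to +14% if relief is bounded at 180 minutes, and from −62% to +3% if it is exponential. The bound borrows the 3 hours cited in Study Purpose and Rationale, which comes from inpatients and is not a proven limit. The exponential shape is assumption only.

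**Step 3: oral wording.** Suppose every patient still below 7 gets an oral dose 30 or 60 minutes before leaving and the dose does not change pain. The Statistical Plan mean then exceeds the Study Design mean by 1 to 30 min (bounded) or 3 to 43 min (exponential). Check of one cell: with T uniform and C on 60–180, a dose 60 min earlier falls on 0–120, so the Study Design mean is 60 − 4,800/360 = 46.7, against 76.7. The gap is 30.

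**Step 4: population.** Assume responders average 90 min and non-responders end at 5 min.

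- Responders only: 90 min.
- 3 of 12 non-responders counted: (9 × 90 + 3 × 5)/12 = 68.75 min.
- 6 of 12 counted: (6 × 90 + 6 × 5)/12 = 47.5 min.

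**Step 5: does censoring departures repair it?** Not if an oral transition made below 7 remains an event. With the dose 60 min before a departure on 60–240, it falls uniformly on 0–180. For uniform relief, the survival curve for return of pain or oral dose is (1 − t/180)², with median 180 × (1 − 0.707) = 53 against a true 90. For exponential relief with median 120 it is 2^(−t/120) × (1 − t/180), with median 56 against 120.

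**The case against.** The best defence is that the outcome is an openly stated composite. Both sections list discharge and admission as end points, the study is a pilot meant to describe the analgesic effect, and no test uses the result. The per-patient plots will partly show who left with pain below 7. This stands as far as it goes: the time itself is a legitimate thing to report. It does not rescue the label, because both sections call it duration of analgesia, it is the only numerical analysis for Aim 2, and a plot does not change the mean.

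A second defence is that no harm has been shown. This also stands in part. A reader might infer that the planned mean must substantially understate the analgesia from N2O. Truncation alone can only lower the mean, but the documents fix neither its size nor, once late detection is allowed for, the sign of the net error. The large losses in the table depend on long exponential tails that nothing in the documents supports.

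A reader might also infer that the plan drops non-responders. The text does not say so. The parenthesis directly follows the return-to-7 end point and most naturally qualifies only that; the fault is that the matter is left open.

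Finally, Kaplan-Meier is no cure with 12 patients. In the same scenarios the median is not reached in 0–2% of trials (bounded) or 0–57% (exponential). Censoring can also be informative. If some patients are admitted shortly before pain returns, the median came out at 157 against a true 120, and at 117 when admission was counted as an event. Censoring is therefore one option, to be read beside the reasons for ending.

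**Conclusion.** The point holds on the text alone. The planned mean and SD treat departure with pain below 7 as completed relief, so those values are lower bounds. The two definitions conflict on which analgesia ends the duration, in a study where an oral transition is foreseen. The handling of patients still at 7 or more after N2O is not settled.

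The size is unknown. The truncation, oral-wording and population figures above are illustrations under stated assumptions, and the net direction of error is uncertain. The outcome is secondary and descriptive; the primary outcome (change in pain score) and the sample size are untouched. It should be fixed, but it does not threaten the main result of the pilot.

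**What to change.** 1. Reconcile Study Design and the Statistical Plan to a single analgesia end point. Which one is for the sponsor to decide.
2. State whether patients still at 7 or more after N2O are included in this outcome. In either case report how many fell below 7 and how many did not.
3. Tabulate, for each patient, why the duration ended (pain 7 or more, parenteral analgesia, oral analgesia, discharge, admission), with the last pain score.
4. Do not present the plain mean as duration of analgesia. Choose one of two routes:
   - Right-censor discharge, admission where scoring stops, and any oral transition made with pain below 7 that would otherwise end the duration. Report a Kaplan-Meier curve with the median if reached, and a sensitivity analysis counting these as events.
   - Keep the mean and SD, relabelled as *observed ED time until pain return, further analgesia or departure*, beside the table in item 3.

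The cost is wording in two sections and one small table. Scores, analgesic times, and the time and type of departure are already needed for the outcome as defined. The downside of the first route is that the median may not be reached and the censoring may be informative; it also does not correct late detection. Under either route the result stays descriptive.
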